## **ABSTRACT**

**OBJECTIVE:** To test the hypothesis that a feeding-bundle concurrent with acid-suppression is superior to acid-suppression alone in improving gastroesophageal reflux disease (GERD) attributed-symptom scores and feeding outcomes in neonatal ICU infants.

**METHODS:** Infants (N=76) between 34-60 weeks' postmenstrual age with acid reflux index>3% were randomly allocated to study (acid suppressive therapy + feeding bundle) or conventional (acid suppressive therapy only) arms for 4 weeks. Feeding bundle included: total fluid volume <140 ml/kg/day, fed over 30 min in right lateral position, and supine postprandial position. Primary outcome was independent oral feeding and/or  $\geq 6$ -point decrease in symptom score (I-GERQ-R). Secondary outcomes included growth (weight, length, head circumference), length of hospital stay (LOHS, days), airway (oxygen at discharge), and developmental (Bayley scores) milestones.

**RESULTS:** Of 688 screened: 76 infants were randomized and used for the primary outcome as intent-to-treat, and secondary outcomes analyzed for 72 infants (N=35 conventional, N=37 study). For study vs conventional groups, respectively: a) 33%(95% CI, 19%-49%) vs 44%(95% CI, 28%-62%), p=0.28 achieved primary outcome success, and b) secondary outcomes did not significantly differ (p>0.05).

**CONCLUSIONS:** Feeding strategy modifications concurrent with acid suppression are not superior to PPI alone in improving GERD symptoms or discharge feeding, short-term and long-term outcomes.

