## STUDY OUTCOMES

### Primary and Secondary Clinical Outcomes

The clinically meaningful primary and secondary outcomes did not differ significantly between groups (**Table 2**). I-GERQ-R scores for study and conventional groups are shown (**Fig 2**). At inception: positive I-GERQ-R was 19/35 (54%) in the conventional group vs 24/37 (65%) in the study group,  $p=0.36$ . At Time-2: positive I-GERQ-R prevalence was 9/31 (29%) in the conventional group vs 13/34 (38%) in the study group,  $p=0.43$ . In the study group vs conventional group, respectively: a) primary outcome achieved in 33% (95% CI, 19% - 49%) vs 44% (95% CI, 28% - 62%) ( $p=0.28$ ), b) secondary outcomes: independent oral feeding in 65% (95% CI, 48% - 80%) vs 77% (95% CI, 60% - 90%),  $p=0.26$ ,  $\geq 6$ -point I-GERQ-R decrease in 38% (95% CI, 22% - 56%) vs 35% (95% CI, 19% - 55%),  $p=0.82$ , length of stay was 98 [81-132] days vs 108 [83-125] days,  $p=0.89$ , and oxygen requirement at discharge in 19% (95% CI, 8% - 35%) vs 26% (95% CI, 13% - 43%),  $p=0.49$ . There were no significant differences in growth metrics (all  $p>0.05$ ) or developmental scores at 2 years (all  $p>0.05$ ). Feeding outcomes or I-GERQ-R scores did not significantly differ between conventional vs study groups based on feeding method at inception (**Table 3**). Individual I-GERQ-R questions relating to vomiting, regurgitation, and crying (i.e. frequency of emesis, volume of emesis, symptoms with emesis, and crying more than usual in the

past week) had no differences ( $P>0.05$ ) within the group or between the groups across maturation for these individual symptoms, except for symptoms with emesis (never: rarely: sometimes: often: always, %) was 16:16:42:19:6 for conventional group at Time-1 vs 18:18:29:0:35 for study group at Time-1,  $p < 0.01$ .

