### **DISCUSSION**

In this RCT, while controlling for birth gestation and severity of acidity, we compared the effectiveness of acid suppression with or without a systematic feeding modification bundle in modifying feeding outcomes and I-GERQ-R scores. We found no differences in our *a priori* primary outcome or pre-assigned secondary outcomes. Important clinical and research implications can be noted despite the non-superiority of the feeding bundle.

Diagnostic conundrums and management issues with GERD in the NICU setting persist. Prior studies (8, 19, 20) used perceived clinical symptoms as a basis for acid-suppression, but studies have shown lack of benefit on symptom improvement (35, 36). Recent work by us (6, 21, 22), suggests that such symptoms are often due to pharyngo-esophageal provocation or cross-systems activation of reflexes, and can occur during non-acid events or swallowing events, or

during transient relaxation of lower esophageal sphincter (30). However, the inability to handle the refluxate determines the ‘troublesomeness of the symptoms’ rather than the esophageal acid exposure. Clinical practice varies when pathophysiological reasoning is not commonly applied. Clinical practices can have unintended consequences (1, 37-40) resulting from acid suppression, undernutrition, delays with feeding milestones, decisional conflicts, discharge outcomes and prolonged hospitalization, all of which can escalate burden (9, 27).

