**Table 2. Primary and Secondary Clinical Outcomes and Compliance Measures**

Primary Outcome (intent-to-treat analysis)	Overall (N = 76)	Conventional (N = 36)	Study (N = 40)	P-value
A priori clinical outcome Success, n (%)	29 (38)	16 (44)	13 (33)	0.28
Secondary Outcomes	Overall (N = 72)	Conventional (N = 35)	Study (N = 37)	P-value
I-GERQ-R decrease by 6 – n (%)	24/65 (37)	11/31 (35)	13/34 (38)	0.82
Feeding Outcome at Time 2 – n (%)				0.26
PO	51 (71)	27 (77)	24 (65)	
Transition (PO + Tube)	18 (25)	8 (23)	10 (27)	
Tube	3 (4)	0 (0)	3 (8)	
Length of hospital stay – days	108 [82 - 128]	108 [83 - 125]	98 [81 - 132]	0.89
Hospital stay Inception to Discharge – days	25 [11 - 45]	23 [3 - 39]	27 [16 - 47]	0.26
Weight Growth Velocity (GV) – g/day	27.1 (9.4)	26.5 (7.2)	27.6 (11.1)	0.64
Length GV – cm/day*	0.1 (0.1)	0.1 (0.1)	0.1 (0.1)	0.88
Head Circumference GV – cm/day*	0.1 [0.0 - 0.1]	0.1 [0.0 - 0.1]	0.1 [0.0 - 0.1]	0.87
Feeding Method at Discharge – n (%)				0.32
PO	54 (75)	29 (83)	25 (68)	
Transition (PO + Tube)	14 (19)	5 (14)	9 (24)	
Tube	4 (6)	1 (3)	3 (8)	
Oxygen Requirement at discharge – n (%)	16 (22)	9 (26)	7 (19)	0.49
Compliance to Feeding Methods				
Total Fluid Volume (TFV)				
TFV at Inception- #	N/A	150 [147, 152]	150 [149, 156]	0.8
TFV at Time 2- #	N/A	143 [134, 148]*	133 [126, 137]*	<0.001
# days TFV ≤ 140 / kg / day	N/A	10 [2, 26]	22 [11, 31]	0.005
TFV compliance (TFV <140/kg/d for >75% of time)	N/A	9 (26)	27 (73)	<0.001
Position				
Feeding Position, RSL, %	N/A	5 [1, 17]	78 [12, 94]	<0.001
Feeding in RSL >75% of the time, %	N/A	0 (0)	21 (57)	<0.001
Supine Position Post-Prandial, %	N/A	50 [40, 66]	87 [74, 96]	<0.001
Supine Position Post-prandial >75% of the time, %	N/A	7/34 (21)	27/36 (75)	<0.001
Feeding Duration				
% time feed duration >30 min, %	N/A	4 [0, 37]	15 [0, 69]	0.15
Feeding Duration at Inception, min	N/A	23 [17, 41]	30 [19, 34]	0.64
Feeding Duration at Time 2, min	N/A	23 [18, 28]	26 [20, 30]	0.15
Long-term Follow-up†				
Feeding Method at 6 months – n (%)				0.65
PO	36/50 (72)	21/27 (78)	15/23 (65)	
Transition (PO + Tube)	10/50 (20)	4/27 (15)	6/23 (26)	
Tube	4/50 (8)	2/27 (7)	2/23 (9)	
Feeding Method at 1 year – n (%)				0.11
PO	37/44 (84)	20/22 (91)	17/22 (77)	
Transition (PO + Tube)	4/44 (9)	0/22 (0)	4/22 (18)	
Tube	3/44 (7)	2/22 (9)	1/22 (5)	
CCABSID-III				
Cognitive Score <80 – n (%)	9/44 (21)	5/23 (22)	4/21 (19)	1.00
Cognitive Score – #	95 [90 - 105]	100 [90 - 105]	90 [90 - 100]	0.11

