## 4.0 Study Endpoints

- Primary Outcome
  - **Clinical outcome of feeding success for those infants transitioning to oral feeds at inception.**
    - The primary endpoint is the feeding success defined as achieving full oral feeds (defined as no need for tube feeds to maintain hydration and nutrition) and/or a  $>/=$  6-point decrease from baseline I-GERQ-R. The time frame is up to 5 weeks after enrollment.
  - **Clinical outcome of feeding success for those infants on full oral feeds at inception.**
    - The primary endpoint is the feeding success defined as maintaining full oral feeds and a  $>/=$  6-point decrease from baseline I-GERQ-R. The time frame is up to 5 weeks after enrollment.
- Secondary Outcomes
  - Clinical Outcomes
    - Length of hospital stay
    - Growth outcomes during the study period and up to 1 year
    - Independent feeding skills over time up to 1 year
    - Respiratory support during the study period and at discharge
    - Developmental outcomes with Bayley's scores at 2 years
    - Individual differences in I-GERQ-R questionnaire
  - Motility Outcomes
    - Mechanisms of aerodigestive clearance and esophageal provocation are evaluated based on esophageal motility studies at inception and after 5 weeks.
  - pH Impedance outcomes
    - 24-hour pH impedance results at inception of study and then 5 weeks later after treatment completed

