### **6.3 Data to be collected**

- Patient diary logs for symptoms, feeding process, medication compliance, physician visits and clinical data.
- 24-hr pH data will be collected to characterize the frequency, acid reflux index, Vandenplas score, longest reflux event duration, and number longer than 5 min
- Basal manometry data will be collected to assess swallow frequency, resting UES and LES pressure, swallow propagation types, peristaltic velocity, frequency of symptoms and the causative mechanisms.
- Multimodal sensory motor testing involves mid-esophageal provocation with graded infusions (0.1 to 5 ml) of air (to stimulate mechanoreceptors), apple juice (pH 3.7, to stimulate acid-sensitive receptors), and sterile water (pH 7.0, as control stimulus), and examine the changes in sensory-motor characteristics of aerodigestive reflexes pertinent to secondary peristalsis or deglutition response, esophago-UES contractile reflex, LES-relaxation reflex, and symptoms during the stimulation. This protocol will be performed in both experimental and standard therapy groups at time-1 and time-2 (where feasible).
- Basal and adaptive pharyngeal reflexes with air and water infusions are measured at time-1 and time-2 (where feasible).
- Subjects will be monitored up to one year through electronic medical records (EPIC) for number of hospital readmissions, number of clinic visits, growth metrics and medication use.

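### Growth to one year is a planned secondary outcome, but growth is reported for the treatment period only, while the abstract and conclusion speak of long-term outcomes

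*Combined protocol and SAP*

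**What the plan says.** Section 4.0 (Study Endpoints) lists among the secondary clinical outcomes "Growth outcomes during the study period and up to 1 year". Section 6.3 (Data to be collected) adds: "Subjects will be monitored up to one year through electronic medical records (EPIC) for number of hospital readmissions, number of clinic visits, growth metrics", together with medication use. Section 6.1 also plans long-term collection of growth.

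In the report, Statistical Methods describes growth velocity between time-1 and time-2, compared between arms by two-sample t-test or Wilcoxon rank-sum test. Table 2 gives three growth rows (weight, length, head circumference), all as velocities. Its long-term block holds feeding method at 6 months and 1 year, followed by the developmental scores. It has no weight, length or head circumference, and no readmissions or clinic visits appear in the text or tables. Under Primary and Secondary Clinical Outcomes the result reads: "There were no significant differences in growth metrics".

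The abstract concludes that the bundle is not superior in improving "discharge feeding, short-term and long-term outcomes". The Conclusion says that no effect was detected on a priori short-term or long-term outcomes.

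**The concern.** The bundle caps feeding volume, and intake did fall in the study arm. Growth is therefore the outcome on which a reader would look for a cost of the intervention, both during treatment and afterwards. The plan foresaw this with a one-year horizon. If that part is missing while the conclusions cover long-term outcomes, a reader will take growth as settled to one year when it was examined only over the treatment window.

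Within that window, the comparison is of means or medians. Equal means are compatible with very different numbers of poorly growing infants, and Table 2 gives no count, minimum or low percentile.

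**Working it through.** **1. Planned against reported**

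| Item | Plan | Report |
|---|---|---|
| Growth, treatment period | 4.0, secondary outcome | Table 2, velocities |
| Growth to 1 year | 4.0, secondary outcome; 6.3, data collection | not given |
| Readmissions, clinic visits to 1 year | 6.3, data collection | not given |
| Feeding skills to 1 year | 4.0, secondary outcome | Table 2, 44 infants at 1 year |
| Development at 2 years | 4.0, secondary outcome | Table 2 |

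None of the eight entries in the IRB revision history removes one-year growth. The report's Outcome Measures section lists growth metrics but leaves out the horizon. The protocol's own horizons differ: 1 year in 4.0 and 6.3, 12 and 24 months in separate statements in 6.1, and 18 months in 6.4. These need to be reconciled.

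**2. Reproducing the weight-gain result**

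Inputs from Table 2 (row "Weight Growth Velocity (GV"): conventional 26.5 (SD 7.2), study 27.6 (SD 11.1) g/day, p = 0.64. The numbers per arm are assumed to be those of the secondary analysis, 35 and 37.

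- Pooled SD = √[(34 × 7.2² + 36 × 11.1²)/70] = 9.41.
- SE = 9.41 × √(1/35 + 1/37) = 2.22; t = 1.1/2.22 = 0.50; p = 0.62. Moving each mean and SD over its rounding interval gives 0.59 to 0.66, so the printed 0.64 is consistent.
- Unequal variances: SE = √(7.2²/35 + 11.1²/37) = 2.19, df = 62, p = 0.62. The difference is 1.1 ± 2.00 × 2.19, that is -3.3 to +5.5 g/day.

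The printed test is correct, and the choice between the pooled and unequal-variance forms makes no difference.

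**3. Spread**

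- SD ratio = 11.1/7.2 = 1.54; variance ratio = 1.54² = 2.38.
- The 2.5% and 97.5% points of F with 36 and 34 df are 0.511 and 1.968. The 95% CI for the variance ratio is 2.38/1.968 to 2.38/0.511 = 1.21 to 4.65; for the SD ratio, 1.10 to 2.16. Two-sided p = 0.013. All of this assumes normality.

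**4. What the spread can and cannot show**

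The SD does not locate the extra spread. Take 34 infants with mean 25.05 and SD 7.2, plus three at 56.49 g/day:

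- mean = (34 × 25.05 + 3 × 56.49)/37 = 27.6;
- SD = √[(33 × 7.2² + (34 × 3/37) × 31.44²)/36] = 11.1.

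These are the printed study-arm figures, with the added spread lying entirely among fast growers. A normal model instead widens both tails: below 15 g/day, 12.8% study vs 5.5% conventional; above 40 g/day, 13.2% vs 3.0%. Both cut-offs are illustrative assumptions, and the shares are modelled, not observed. The printed figures fit either picture.

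**5. Length and head circumference**

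Both are printed to 0.1 cm/day. A printed 0.1 covers 0.05 to 0.15, or 0.05 × 28 = 1.4 cm to 0.15 × 28 = 4.2 cm over 28 days. Differences in centre or spread within that range cannot be seen in the table.

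**6. How complete one-year data could be**

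Feeding method at 1 year is known for 22/36 = 61% (conventional) and 22/40 = 55% (study), or 44/76 = 58% overall. At 6 months it is 50/76 = 66%.

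**The case against.** The strongest case on the other side has four parts.

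*The long-term claim is not about growth.* Outcome Measures attaches its long-term wording to feeding and development, and both are reported. That is a fair reading of that section. The Conclusion, however, refers to a priori long-term outcomes without restriction, and the a priori list in section 4.0 includes one-year growth. The wording is broader than the data shown.

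*Readmissions and visits are items to collect, not section 4.0 endpoints.* This stands, and they rank below one-year growth. Sections 2.2 and 3.3 do name resource utilization among the secondary measures without defining it, so the counts are not foreign to the plan.

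*The spread comparison is an unplanned look at one row of a long table, and the F test depends on shape.* This stands. With equal true variances, simulation gives a ratio at least this extreme about 1.3% of the time for normal data, 3% for gamma, 4% for t with 8 df and 6% for lognormal (the last three shapes are assumed). The study arm also had more full-term infants (6/40 vs 2/36) and a wider postmenstrual-age SD (2.7 vs 2.2 weeks), which might contribute to the spread.

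*Nothing shows harm.* Also correct: the mean is slightly higher in the study arm. A reader might infer that slow growers were more frequent there and that the means hide them. Step 4 of the working shows that the SDs do not support this. A reader might also take undernutrition to be the documents' named risk of volume restriction. The Discussion phrase "acid suppression, undernutrition, delays with feeding milestones" belongs to a list of consequences of clinical practice in general, and section 14.0 names only catheter placement.

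**Conclusion.** The concern holds as an outcome-reporting gap with a conclusion wider than the evidence. A planned secondary outcome, growth to one year, is absent from the text and tables, as are the planned one-year readmission and visit counts. The growth statement is supported only for mean or median velocity over the treatment period. For weight, that means a difference of +1.1 g/day with a CI of -3.3 to +5.5.

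Lower intake in the study arm and an SD ratio of 1.54 (1.10 to 2.16, under normality) are reason enough to show the distribution. They are not evidence of poor growth.

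Two limits apply. "Not reported" means not found in the available text and tables; figures are not shown. And the documents establish that one-year growth was planned, not that it was captured, so they do not support an inference that collected data were withheld.

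**What to change.** 1. Report weight, length and head circumference at one year by arm, with CIs and the number of infants with data, plus the one-year readmission and clinic-visit counts. If any of these was not captured, say so.
2. Until then, restrict the growth sentence to mean or median growth velocity over the treatment period, and state in the abstract and Conclusion that the long-term result covers feeding method and development, not growth.
3. Show the weight-gain distribution by arm, with at least the minimum and 10th percentile, labelled post hoc. A low-gain cut-off can no longer be fixed in advance, since the data are locked and analysed.
4. Reconcile the growth follow-up horizons in sections 4.0, 6.1, 6.3 and 6.4.

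The cost is a few table rows and wording changes if the records exist, and one sentence if they do not. The downside is incompleteness: if growth was captured about as often as one-year feeding method (44 of 76), the estimates will be imprecise and open to selective follow-up, and should be labelled so.

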## OUTCOME MEASURES

The *a priori primary end-point* was achieving independent oral feeds and/or a six-point decrease in I-GERQ-R score at 5 weeks or sooner, whichever was earliest at discharge. *To clarify further, there were 2 scenarios:* 1) Among infants who were transitioning to oral feeds (gavage fed) at inception: success was defined as achieving full oral feeds or a  $\geq 6$ -point decrease from baseline I-GERQ-R. 2) Among infants who were on full oral feeds at inception, success was determined if full oral feeds were maintained plus a  $\geq 6$ -points decrease from baseline I-GERQ-R. *Secondary end-points* included growth metrics (weight, length and head circumference), supplemental oxygen, economic metrics (LOHS), long-term feeding outcomes at 6 months and 1 year, and developmental outcomes at 2 years (32, 33).

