**Table 1. Baseline Demographic and Clinical Characteristics of Enrolled Participants**

Variable	Overall Subjects (N = 76)	Conventional Group (N = 36)	Study Group (N = 40)
At Birth			
Gender, Female – n (%)	37 (49)	18 (50)	19 (48)
Race – n (%)			
African American	11 (15)	3 (8)	8 (20)
Asian	1 (1)	0 (0)	1 (3)
Other	6 (8)	2 (6)	4 (10)
Unknown	1 (1)	1 (3)	0 (0)
White	57 (75)	30 (83)	27 (68)
Ethnicity – n (%)			
Hispanic or Latino	2 (3)	2 (6)	0 (0)
Non Hispanic or Latino	71 (93)	32 (89)	39 (98)
Unknown	3 (4)	2 (6)	1 (3)
Gestational Age (GA) – wks	29.3 [27 - 32.9]	29.3 [28 - 32.2]	29.2 [27 - 33.1]
Preterm birth – n (%)	68 (90)	34 (94)	34 (85)
Birth Weight – kg	1.23 [0.9 - 1.9]	1.2 [0.9 - 1.9]	1.3 [0.9 - 2.1]
Size for Gestational Age – n (%)			
Small (< 10th %)	9 (12)	5 (14)	4 (10)
Average (10th - 90th %)	58 (76)	26 (72)	32 (80)
Large (> 90th %)	9 (12)	5 (14)	4 (10)
Cesarean Delivery – n (%)	50 (66)	22 (61)	28 (70)
At Inception			
Postmenstrual age – wks	41.1 (2.5)	41.3 (2.2)	40.9 (2.7)
Chronologic age – wks	10.9 (4.3)	11.1 (4.5)	10.7 (4.3)
Weight – kg	3.5 (0.8)	3.5 (0.8)	3.5 (0.8)
O 2 Requirement at 36 wks PMA – n (%)	36 (47)	17 (47)	19 (48)
O 2 Requirement at 28 days age – n (%)	46 (61)	21 (58)	25 (63)
Feeding Method – n (%)			
Gavage	2 (3)	0 (0)	2 (5)
Transitional	37 (49)	18 (50)	19 (48)
Oral	37 (49)	18 (50)	19 (48)
Nasal Cannula Oxygen – n (%)	23 (30)	11 (31)	12 (30)
Total Intake Volume – mL/kg/day	150 [149 - 154]	150 [148 - 152]	150 [150 - 157]
Total Oral Intake Volume – mL/kg/day	112 [45 - 150]	112 [57 - 150]	112 [22 - 148]
Acid Reflux Index (ARI) – %	9.3 [6.0 - 17.1]	10 [6.0 - 16.7]	9.1 [5.0 - 17.6]
ARI Category – n (%)			
Indeterminate (ARI 3 - 7%)	26 (34)	12 (33)	14 (35)
Abnormal (ARI > 7%)	50 (66)	24 (67)	26 (65)

Data presented as n (%), Median [IQR], or Mean (SD).

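### Respiratory support is planned for two windows, but the report gives only oxygen at discharge, from an unadjusted test with no between-arm interval

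*Combined protocol and SAP*

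**What the plan says.** Protocol section 4.0 (Study Endpoints, Clinical Outcomes) lists "Respiratory support during the study period and at discharge". It does not define an event or a summary measure for the study-period part. Section 3.3 says that every secondary variable will be analysed by mixed or logistic regression, with potential confounders included. The confounders it names are medications, feeding position or volume, and feeding method. Oxygen at entry is not among them.

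In the report, the Abstract defines the airway outcome as oxygen at discharge, and Outcome Measures lists supplemental oxygen without a time. Statistical Methods says that supplemental oxygen was compared by Fisher's exact or chi-square test. The only respiratory row among the outcomes in Table 2 is "Oxygen Requirement at discharge": 9 of 35 conventional and 7 of 37 study infants. Study Outcomes gives an interval for each arm and p=0.49, but no interval for the difference. Table 1 shows "Nasal Cannula Oxygen" at inception for 11 of 36 conventional and 12 of 40 study infants. None of the eight entries in the IRB revision history drops the study-period window.

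**The concern.** One half of a pre-specified outcome is missing from the report without explanation, yet the opening of the Discussion says that the pre-assigned secondary outcomes showed no differences. A reader would take that to cover respiratory support over the treatment weeks.

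The half that is reported is also hard to interpret. It is read at whatever day the infant went home. It is tested without the planned model, and a p-value of 0.49 does not tell the reader how large a difference the data leave open. Oxygen at inception is a natural baseline variable for this comparison and had already been collected, but it plays no part in the outcome analysis.

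**Working it through.** **1. Reproduce the reported result.** Inputs from Table 2: 7/37 study, 9/35 conventional. Pearson chi-square without correction = 72 × (7×26 - 30×9)² / (37×35×16×56) = 557,568 / 1,160,320 = 0.48, p = 0.49. Exact intervals are 8.0% to 35.2% and 12.5% to 43.3%. All agree with the report. The continuity-corrected test (p=0.68) and Fisher's test (p=0.58) do not, so the plain chi-square was used.

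**2. The difference that the report leaves out.** p1 = 7/37 = 0.189 and p0 = 9/35 = 0.257, so the difference (study minus conventional) is -6.8 points. SE = √(0.189×0.811/37 + 0.257×0.743/35) = 0.098, or 9.8 points. The 95% CI is -6.8 ± 1.96×9.8 = -26.0 to +12.4 points.

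**3. Can discharge stand in for the study period?** Table 2 gives inception-to-discharge stay as 23 [3-39] days conventional and 27 [16-47] days study (p=0.26), against a five-week period. About a quarter of conventional infants were read within 3 days of inception, close to baseline. In each arm at least a quarter were read after week 5 (upper quartiles 39 and 47 days). There is no common reading time.

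**4. Who is counted.** The analysis set lost 1 conventional infant (36 to 35) and 3 study infants (40 to 37). Even if all four had been on oxygen at entry, at least 11-1 = 10 conventional and 12-3 = 9 study infants in the set were on it, which is 19/72 (26%). At discharge the counts are 9 and 7, or 16/72 (22%). So at least (10-9) + (9-7) = 3 infants had oxygen at the start of the study period and are not counted at discharge. Oxygen started after entry is not shown.

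**5. What stratifying by entry oxygen could gain.** The entry-by-discharge table is not reported, so it is assumed. With strata k (on or off oxygen at entry), w_k = n1k·n0k/(n1k+n0k), the Mantel-Haenszel difference is Σw_k·d_k/Σw_k, and SE = √(Σw_k²·v_k)/Σw_k, where v_k is the usual binomial variance of d_k.

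Example: 11 per arm on oxygen at entry, with 14 of the 16 discharge-oxygen infants among them (6 study, 8 conventional).
- On oxygen: 6/11 vs 8/11, w = 5.5, v = 0.0406.
- Off oxygen: 1/26 vs 1/24, w = 12.48, v = 0.0031.
- Difference = (5.5×(-0.182) + 12.48×(-0.003))/17.98 = -5.8 points.
- SE = √(30.25×0.0406 + 155.75×0.0031)/17.98 = 7.3 points.

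Other assumed tables (11 conventional and 11 or 12 study infants on oxygen at entry):

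| Discharge-oxygen infants also on oxygen at entry (study + conventional) | SE, points | 95% CI with 11 study | 95% CI with 12 study |
|---|---|---|---|
| 16 of 16 (7+9) | 5.7-5.9 | -16.7 to +5.6 | -19.0 to +4.0 |
| 14 (6+8) | 7.3-7.4 | -20.0 to +8.5 | -21.8 to +7.1 |
| 12 (5+7) | 8.3-8.4 | -22.3 to +10.3 | -23.7 to +9.2 |
| 10 (4+6) | 9.0-9.1 | -23.9 to +11.5 | -24.9 to +10.7 |
| 5 (2+3) | 9.8 | -26.0 to +12.4 | -26.0 to +12.4 |

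At the lowest possible entry counts (10 conventional, 9 study) the SE is 4.4, 6.6, 7.9, 8.8 and 9.8 points in the same five rows. No interval in any of these scenarios excludes zero.

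**6. The planned logistic model.** The unadjusted odds ratio is 0.67 (0.22-2.06), with SE of the log odds ratio 0.571. With 11 per arm on oxygen at entry, adjustment gives SE 0.769 at 14 of 16, 0.669 at 12 and 0.615 at 10. The interval widens because the odds ratio is not collapsible. This is not a loss of power.

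**The case against.** Discharge is one of the protocol's own time points, so reading oxygen then follows the plan. Where the Discussion speaks of respiratory support or oxygen specifically, it limits the statement to discharge. A reader might infer that the report claims no respiratory difference over the study period; only the general sentence about pre-assigned secondary outcomes reaches that far. This narrows the point to that sentence and to the missing result.

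Four other stronger readings are not supported:
- **That the discharge date depends on the arm.** The stays overlap and p=0.26. What stands is the lack of a common date.
- **That 23/76 at entry can be set against 16/72 at discharge.** The denominators differ. The supported comparison is at least 19/72 against 16/72. Entry oxygen also precedes treatment, so an any-oxygen measure would count those infants as events from the first day whatever their arm.
- **That leaving out entry oxygen biases the result.** It was 31% and 30% by arm, and the plan does not name it as a covariate.
- **That the uncertainty is shown to be larger than necessary.** The report gives no between-arm interval, and the gain rests on an unreported table. The large gain, (9.8/5.8)² or nearly three times the sample, needs all 16 discharge-oxygen infants to have been on oxygen at entry. Near 5 of 16 it disappears.

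It is also fair to say that study-period data may be incomplete. Median stay from inception was 25 days, so more than half the infants were home before week 5, and protocol section 6.1 says that the data then depend on parents. Section 6.3 does not name respiratory support among the items collected.

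**Conclusion.** The point holds as a reporting and analysis gap in one secondary outcome. The study-period component is pre-specified and unreported, and no listed revision removes it. The planned regression was replaced by an unadjusted test. The discharge result is compatible with anything from 26 points fewer to 12 points more infants on oxygen in the study arm, so it does not establish that the arms are alike. At least 3 infants with oxygen at the start of the study period are outside the discharge count.

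The case for stratifying by entry oxygen is one of precision only. It rests on entry and discharge oxygen being associated, which is plausible but not shown. In none of the scenarios worked through would stratifying turn the result into evidence of a difference.

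**What to change.** (a) Report respiratory support during the study period by arm. Oxygen status at Time 2 is preferable to any oxygen, because it does not count entry oxygen as an event. Say how many readings after discharge rely on parent report and how many are missing. If the data cannot support this, state that the component was not analysed and limit the no-difference statements to discharge.

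(b) Give the entry-by-discharge oxygen table by arm, and a Mantel-Haenszel or standardised risk difference with 95% CI, stratified by nasal cannula oxygen at inception. If the planned logistic model is also reported, do not present it as the more precise analysis.

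Part (b) needs only the two oxygen readings already reported. Part (a) needs extraction from inpatient records and, for infants already home, from diaries and calls with parents, where gaps are likely. Neither part needs a new study procedure.
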